## 10.2 Validation of the SBQ-LC™

Anonymised PRO data collected via the Aparito Atom5™ digital platform during WP1 will be downloaded from the Aparito cloud at multiple time points as a csv file, cleaned and prepared for statistical analyses. A range of statistical analysis software packages will be used to undertake Rasch analysis, report descriptive item/scale characteristics (e.g., response frequency, means, skewness, kurtosis), and to undertake psychometric analyses using traditional methods including evaluation of internal consistency, reliability, test-retest reliability, construct/criterion validity, measurement error, and responsiveness. Analysis will be led by one researcher and discussed and verified by a second researcher with expertise in PRO development and psychometrics. The analysis plan is described below:

### Sample and item characteristics

Demographic characteristics of participants will be reported using descriptive statistics (i.e., frequency counts). Per item, distribution of responses across response categories, score means, skewness, kurtosis, and presence of floor/ceiling effects) will be reported.

### Rasch analysis

To confirm fit of the SBQ-LC™'s items to the Rasch model for interval-level measurement, a range of statistical and graphical analyses will be performed for each scale/subscale:

*Assessment of rating scale functioning* - As greater symptom burden should equate to higher scores on the SBQ-LC™, it is expected that the higher the level of severity, frequency or interference, the higher the response category that will be endorsed. Items will be inspected to ensure that all items orient with the latent variable. Response category thresholds will be inspected to confirm that categories advance monotonically across the measurement continuum. The item category probability curves (CPC) will be inspected for threshold ordering. We will check that each response category is endorsed by a minimum of ten persons per response category. Outfit MNSQ values  $< 2.0$  logits will be considered evidence of acceptable category fit.

*Assessment of item and person fit to the model* - Fit statistics show the extent that item performance and person ability differ from the Rasch modelled expectations. Item fit will be confirmed by inspecting the item characteristic curves (ICCs) for each item. The empirical and model ICCs should present a close alignment of the observed and predicted scores for an item. Person fit will be assessed in the same manner as item fit. Infit and outfit statistics with mean square values outside the 0.5 – 1.5 logit range will be considered evidence of misfit. Misfitting persons will be removed from the dataset and the Rasch analysis repeated to ascertain the impact of misfitting persons to the analysis.

*Assessment of unidimensionality and local independence* - Unidimensionality (i.e., the set of items under assessment represents a single construct) and local independence of items are core requirements of the Rasch model. Unidimensionality will be assessed using a principal component analysis of the residuals (PCAR). The following criteria will be applied as evidence of unidimensionality:

1. an eigenvalue less than 3.0 on the first residual contrast
2. The percentage variance explained by the first contrast of 5% or less
3. Disattenuated correlations between the person measures for the item clusters on the first residual contrast greater than 0.70^40

Local independence will be appraised by examining item fit statistics for overfit and correlations between items of the standardised residuals. Overfit and a substantial correlation of the standardised residuals for two items will be considered evidence of local dependence. A range of critical values for residual correlations have been reported in the literature. For this study, COSMIN-recommended residual correlation values of  $r < 0.2$  will be considered evidence of low dependency.

*Assessment of differential item functioning (DIF)* – Measurement invariance is a criterion of the Rasch model and is established through assessment of DIF. The items of the SBQ-LC™ will be evaluated for DIF for the sample characteristics of gender and age. If possible, and depending on the sample, exploration of cross-cultural DIF and DIF for groups classified according to comorbidity will also be undertaken. DIF contrast values (i.e., effect size) for establishing statistically significant DIF ( $p \leq 0.05$ ) will be based on the size of the reference and focal groups.

*Targeting of the scale* - Targeting assesses the ability of an instrument's items to measure the full range of persons in a sample. Items should collectively form a hierarchy of symptom burden. The item hierarchy should range from the item representing the least burden to the item measuring maximum burden measured using log-odds units or logits. Targeting of the SBQ-LC™'s scales will be assessed by inspecting: 1) the person-item distribution map 2) the summary statistics of item and person measures; and 3) the location range for items and persons on the Rasch scale.

*Assessment of reliability* - Reliability will be evaluated in Winsteps using separation indices. Separation indices indicate the number of distinct levels of functioning that can be distinguished for both items and persons. A person separation index of 1.50 may be considered to represent an acceptable level of separation, whereas an index of 2.00 to represent a good level of separation and index of 3.00 represent to an excellent level of separation. A second statistic, the person reliability index, indicates the replicability of person ordering if the same sample were given another set of parallel items measuring the same construct. Higher values are indicative

of better reliability with values exceeding thresholds of 0.7, 0.8, and 0.9 indicating “acceptable”, “good”, and “excellent” replicability. Item separation will be reported in the same manner as person separation.

#### Internal Consistency Reliability

Internal consistency reliability, a measure of how closely related a set of items are as a group, will be evaluated by computing Cronbach’s alpha ( $\alpha$ ) for each unidimensional scale of the SBQ-LC™. Alpha values greater than 0.70 in addition to confirmed fit to the Rasch model will be considered evidence of good internal consistency reliability.

#### Test-retest reliability

Scale-level intra class correlations (ICCs) using a two-way mixed effects model with absolute agreement and its 95% confidence interval will be specified. A mixed effects model was selected over a random effects model as the test-retest time points will be fixed ( $\pm 7$  days). An ICC coefficient value  $\geq 0.7$  will be considered evidence of adequate reliability. Respondents whose symptoms have remained stable and report that they have not started any new treatment for their Long COVID symptoms within the last four weeks will be included in analyses of test-retest reliability.

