## 8.0 Study procedures

### 8.1 Population-based representative cohort of individuals with long COVID and matched controls

Eligible individuals who wish to participate will download the Aparito Atom5™ app or visit the website and register using their unique one-time use on-boarding code. They will then be asked to provide electronic consent on the app or website, which includes confirming that participants with a positive SARS CoV-2 RT-PCR result have not been hospitalised within 28 days of being diagnosed with COVID-19. Control participants will be asked if they have ever had COVID-19 to check eligibility for inclusion as a control subject. Once the consent form has been completed, participants will be asked to complete a brief demographic and clinical questionnaire. The questionnaire will ask for the following details: name, sex, date of birth, contact number, postal address, ethnic group, GP address, height, weight, smoking status, pregnancy status, SARS CoV-2 vaccination status, confinement (shielding) status, care home residence, occupation, occupational status (in work, furlough, etc.), and over-the-counter medications used to manage symptoms. Full details of these questions are provided in the appendix (Baseline data collection in Atom5™) and in Table 1.0.

Participants will then be invited to report the presence of established Long COVID symptoms and quality of life using validated tools at monthly intervals for a period of 12 months. At each time point, participants will be asked to confirm their willingness to continue to participate in the study. Those wishing to withdraw will be asked to complete a withdrawal form and advised that any data collected up to that point will need to be retained as it will have been used in aggregated data analyses.

As requested by our PPI group, we will ensure that people who are unable to use the app or website (due to no access to a smartphone or internet connection, patient preference, language, or other requirements) can participate through nurse interview-led appointments (telephone or video conference) with translators as required. Information and contact numbers will be provided on the PIS. Alternative language versions of each PRO will be provided where validated translations exist (see table below) The translated questionnaires are currently being programmed on the app.

	English	Bengali	Polish	Welsh	Punjabi	Gujarati	Urdu
EQ5D5L	X	X	X	X	X	X	X
FACIT F	X	X	X		X	X	X
PHQ-2	X	X	X		X	X	
GAD-2	X		X		X	X	X

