PCL-2	X						
modified MRC Dyspnoea Scale	X						
COVID-19 core outcome measure for recovery	X						
SBQ-LC	X						

All participants will be advised where to seek additional support should completion of the PROs raise any concerns regarding their well-being. Proxy-completion will be permitted via the app or website, or via telephone if the participant is unable to complete the PRO and will be documented on the app or website, or via the clinical portal.

Participants will be sent push notification reminders each month to complete the questionnaires on the day completion is due, at 2 days and again at 6 days. Both research personnel and patients will be provided with training resources and telephone support to help minimise missing data. Aparito will provide up to a maximum of two training sessions to the site staff online. A training video will be made available for those that need training after those two sessions. Finally, the site staff will be made aware of the IT support procedures and how to contact Aparito as needed. Aparito will be responsible for providing first line support only to the clinical team via UoB during the duration of the project. Training leaflets outlining how to download and use the app will be provided to staff and patients.

The health service use (primary care consultations, prescriptions, A&E attendances and hospital admissions) and mortality of patients from each Long COVID syndrome will also be described using data from CPRD Aurum and linked data from Hospital Episode Statistics and Office for National Statistics mortality statistics (via CPRD). We aim to use the most up-to-date healthcare data available from CPRD available up to 12 months of follow-up from initial registration on Atom5™.

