## 9.0 Data collection

### 9.1 Questionnaire data collection

Table 1.0-Summary of data collection

	Study time point												
	Baseline (BL)	1 M	2 M	3 M	4 M	5 M	6 M	7 M	8M	9 M	10 M	11 M	12 M
Consent	✓												
Confirmation of COVID-19 infection†	✓	✓	✓	✓	✓	✓	✓	✓	✓	✓	✓	✓	✓
Confirmation of hospital admission within 28 days of COVID-19‡	✓												
Name	✓												
Date of birth	✓												
Telephone number	✓												
e-mail address	✓												
Postal address	✓												
Sex at birth	✓												
Ethnic group	✓												
GP details	✓												
Height	✓												
Weight	✓												
Smoking status	✓												
Pregnancy status¥	✓												
SARS CoV-2 vaccination status	✓	✓	✓	✓	✓	✓	✓	✓	✓	✓	✓	✓	✓
Shielding status	✓												
Care home residence	✓												
Occupation	✓												
Occupational status	✓							✓					✓
Change in duration of working/education	✓												
Reason for change in working or education	✓												
Over-the-counter medication use	✓												

	Study time point												
	Baseline (BL)	1 M	2 M	3 M	4 M	5 M	6 M	7 M	8M	9 M	10 M	11 M	12 M
SBQ-LC™	✓	✓	✓	✓	✓	✓	✓	✓	✓	✓	✓	✓	✓
FACIT-Fatigue	✓	✓	✓	✓	✓	✓	✓	✓	✓	✓	✓	✓	✓
Modified MRC Dyspnoea Scale	✓	✓	✓	✓	✓	✓	✓	✓	✓	✓	✓	✓	✓
COVID-19 core outcome measure for recovery	✓	✓	✓	✓	✓	✓	✓	✓	✓	✓	✓	✓	✓
PHQ-2	✓	✓	✓	✓	✓	✓	✓	✓	✓	✓	✓	✓	✓
GAD-2	✓	✓	✓	✓	✓	✓	✓	✓	✓	✓	✓	✓	✓
PCL-2	✓	✓	✓	✓	✓	✓	✓	✓	✓	✓	✓	✓	✓
EQ-5D	✓	✓	✓	✓	✓	✓	✓	✓	✓	✓	✓	✓	✓
Bio-Sampling*					✓								
Garmin Wearable Device*					✓					✓			

† Only for controls

‡ Only for cases

¥ Only for females

\*Participants selected for bio-sampling and wearable Garmin devices. Data will be recorded from the Garmin devices at baseline (when the devices are provided) for 4 weeks, then 6 months and 12 months on.

Questionnaires will contain the unique Global ID and participant identifiable data (e.g. name, date of birth, address) will be stored separately from research data within the Atom5™ platform and will be accessible only to designated research staff for the purpose of contacting participants for research visits, registering participants at University Hospitals Birmingham for bio-sampling appointments, and where participants report severe Long COVID symptoms and may need advice or support.

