Participants will complete the questionnaires monthly within a timeframe window of -/+ 7 days. Reminders/notifications will be sent by Atom5™ at Baseline/+2 days/+6 days for the baseline questionnaires and at -7 days/0/+2 days for subsequent ones.

At registration, all participants will be asked to provide the onboarding code provided in their invitation letter. Once participants have registered and provided informed consent, they will then be invited to provide baseline demographic data and report the presence of a wide range of symptoms, quality of life and work/education capability using validated tools via the Atom5™ platform.

Patient-reported outcomes will be assessed using symptom specific measures (Table 1): Symptom Burden Questionnaire-Long COVID (SBQ-LC™), FACIT-Fatigue, modified MRC Dyspnoea Scale, COVID-19 core outcome measure for recovery, Patient Health Questionnaire-2 (PHQ-2), Generalized Anxiety Disorder-2 (GAD-2), Abbreviated PTSD Checklist (PCL-2), and quality of life using the EuroQol-5D (EQ-5D).

The SBQ-LC™ will undergo further validation during the study. The development and initial validation of SBQ-LC™ has been applied for through a separate ethics application to the University of Birmingham Research Ethics Committee since participants will not be recruited via the NHS. The SBQ is a disease-specific, multi-domain instrument that will be used to assess symptom burden and functional status (interference). Respondents will be asked to indicate the presence of a symptom over the last 7 days and then provide an indication of symptom burden by providing a response on a 5-point ordinal scale measuring either symptom severity, symptom frequency, or interference. Higher scores will be indicative of greater symptom burden and interference.

The Functional Assessment of Chronic Illness Therapy –Fatigue Scale (FACIT-Fatigue) is a 13-item measure that assesses self-reported fatigue and its impact upon daily activities and function. It has been validated for use across a range of populations. The FACIT-Fatigue has a 7-day recall period and is scored on a 5-point Likert Scale from “0-Not at all” - to “4-Very much”. Individual items scores are summed (two items of which are reverse scored), multiplied by 13 and then divided by the number of items answered, with a higher score indicating less fatigue and better quality of life. It takes less than 5 min to complete.

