The modified MRC Dyspnoea Scale is a modification to the widely used MRC Dyspnoea scale. The item has a 24-hour recall period and is scored on a 5-point Likert scale from “0 - I only get breathless with strenuous exercise” to “4 - I was breathless when dressing, talking or at rest”. It has a high degree of conceptual overlap with its parent clinical measure, the MRC Dyspnoea scale, which is in wide-scale clinical practice.

The COVID-19 core outcome measure for recovery is a single item intending to measure a return to the pre-illness state. The item has a same day recall period and is scored on a 5-point Likert scale from “0 - Completely recovered” to “5 - Not recovered at all”.

The Euroqol EQ-5D-5L comprises five items plus one visual analogue scale. It has been widely validated and used to assess health outcomes from a wide variety of interventions on a common scale for purposes of evaluation, allocation and monitoring. It is used by the National Institute for Health and Care Excellence (NICE) in health technology assessment. EQ-5D-5L takes only a few minutes to complete and has a same day recall period.

The GAD-2 is a screening tool for generalised anxiety disorder derived from the GAD-7. It comprises the first 2 items of the GAD-7, which are considered as the core anxiety symptoms (“feeling nervous, anxious or on edge”/Not being able to stop or control worrying”). The GAD-2 performs well as a screening tool for three other common anxiety disorders (panic disorder, social anxiety disorder, and PTSD). It has a recall period of two weeks. The GAD-2 has a global score (0-6, no weighting). A higher score indicates an increased likelihood of underlying anxiety disorder. The recommended cut-off score for further investigation is  $\geq 3$ . The GAD-2 has been validated in many studies and has retained the same psychometrics properties of the GAD-7 (86% sensitivity/83% specificity)

The PHQ-2 is a screening tool for depression derived from the PHQ-9. It comprises the first 2 items of the PHQ-9 (depressed mood and anhedonia). The PHQ-2 has a recall period of 2 weeks. It has a global score (0-6, no weighting). A higher score indicates an increased likelihood of an underlying depressive disorder. The recommended cut-off score for further investigation is  $\geq 3$ . The PHQ-2 has been validated in many studies and has shown a sensitivity of 83% and specificity of 92%.

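### The test-retest set requires a report of no new Long COVID treatment, but the listed schedule has no treatment question after baseline

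*Protocol*

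**What the plan says.** Section 10.2 (Test-retest reliability) sets two joint conditions for the analysis set: symptoms have stayed stable, and respondents report that "they have not started any new treatment for their Long COVID symptoms within the last four weeks". The pass mark is an ICC of at least 0.7. The next subsection derives the SEM and SDC from a test-retest design as well.

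The data source is this study's own: "Anonymised PRO data collected via the Aparito Atom5™ digital platform during WP1 will be downloaded". Section 9.1 fixes the spacing: "Participants will complete the questionnaires monthly within a timeframe window of -/+ 7 days".

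On treatment, Table 1.0 has one related row, "Over-the-counter medication use", ticked at baseline only. Section 8.1 agrees. It puts the question in the entry questionnaire ("occupational status (in work, furlough, etc.), and over-the-counter medications used to manage symptoms") and then describes the monthly contacts: "Participants will then be invited to report the presence of established Long COVID symptoms and quality of life using validated tools at monthly intervals".

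**The concern.** The second condition is a participant report, and the listed follow-up does not ask for it. The condition exists to keep out people whose scores may have moved because a treatment began between the two administrations. Without it, the first condition is the only safeguard. Any starter whose symptom score moved but who still counts as stable adds real change to what the analysis treats as error. That lowers the ICC and raises the SEM and SDC.

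Validating the SBQ-LC is Objective 2, and the ICC is judged against a fixed threshold. The answer also cannot be reliably recovered once the monthly data have been gathered without the question.

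**Working it through.** **1. Rule against schedule.** The rows of Table 1.0 with any tick after baseline are:

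- infection confirmation (controls only)
- vaccination status
- occupational status (two later time points)
- the eight PROs
- bio-sampling and the wearable device (selected participants)

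Out of 12 follow-up time points, the SBQ-LC is scheduled at 12, a new-treatment item at 0 and over-the-counter use at 0. Any retest pair includes at least one follow-up time point, so the baseline row cannot serve. That row also asks about use rather than new starts, and only about over-the-counter products.

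**2. Possible substitutes in the protocol.**

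- The monthly recovery item: "The COVID-19 core outcome measure for recovery is a single item intending to measure a return to the pre-illness state". It could support the stability condition, although section 10.2 names no anchor. It says nothing about treatment.
- Linked records: "The health service use (primary care consultations, prescriptions, A&E attendances and hospital admissions) and mortality of patients" are to be described from CPRD and linked data. Prescriptions are not participant-reported, and they miss over-the-counter and non-drug treatment.

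**3. Interval against the four-week look-back.** Taking a month as 30 days, two monthly questionnaires with ±7-day windows can be 30 − 14 = 16 to 30 + 14 = 44 days apart. Four weeks is 28 days, so up to 44 − 28 = 16 days of the interval could fall outside a four-week question.

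**4. Upper bound on the effect.** The protocol gives no figure to reproduce. Assume total SD 1, true ICC 0.75 (error variance 0.25, SEM 0.50), a share p of starters who improve by δ SD independently of their score, and no stability screen. For two administrations:

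- ICC (absolute agreement) = 0.75 / (1 + pδ²/2)
- SEM = SD of the difference / √2 = √(0.25 + p(1−p)δ²/2)

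| p | δ | ICC | SEM | SEM rise |
|---|---|---|---|---|
| 0.20 | 0.5 | 0.75/1.025 = 0.73 | √0.2700 = 0.520 | 4% |
| 0.20 | 0.8 | 0.75/1.064 = 0.70 | √0.3012 = 0.549 | 10% |
| 0.30 | 0.5 | 0.75/1.0375 = 0.72 | √0.2763 = 0.526 | 5% |
| 0.30 | 0.8 | 0.75/1.096 = 0.68 | √0.3172 = 0.563 | 13% |

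With a true ICC of 0.80 the worst case is 0.80/1.096 = 0.73.

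**5. With a stability screen.** If the screen removes a share r of starters, the remaining share is p′ = p(1−r)/(1−pr).

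- Worst case (p = 0.30, δ = 0.8), r = 0.5: p′ = 0.15/0.85 = 0.176, ICC = 0.75/1.056 = 0.71, SEM up about 9%.
- Worst case, r = 0.8: p′ = 0.06/0.76 = 0.079, ICC = 0.75/1.025 = 0.73, SEM up about 5%.
- Mildest case (p = 0.20, δ = 0.5), r = 0.5 and 0.8: ICC about 0.74 and 0.75, SEM up about 2.4% and 1.1%.

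The values of r are assumptions too.

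**The case against.** The strongest reply has three parts.

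*The item may exist.* Table 1.0 is titled as a summary and is not exhaustive. Section 8.1 has participants confirm at each time point that they wish to continue, and no row shows it. The Atom5 questionnaires are listed in the appendices but not reproduced, and the rule's own wording implies that respondents will be asked. This stands. A reader might infer that no follow-up contact collects treatment status at all; the documents do not support that. They support only that the required item is absent from Table 1.0 and from the description in section 8.1, which agree with each other.

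*The first condition already does most of the work.* People who improve by 0.5-0.8 SD are those a stability screen is meant to remove. This also stands, and it makes the table in step 4 an upper bound. A reader might infer that the ICC would fall below 0.7. Only the corner with 30% starters and 0.8 SD does so, and it no longer does once half the starters are screened out. Nothing in the protocol supports those starter shares or effects.

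*The detail could be left to an analysis plan, or to the separate SBQ-LC study mentioned in section 9.1.* This does not stand. An analysis plan can define how the stable set is derived, but it cannot supply an answer that was not collected. Section 9.1 also says that validation continues within this study, and section 10.2 bases it on WP1 data.

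**Conclusion.** The point holds as a mismatch between an analysis rule and the listed data collection: on that schedule, the no-new-treatment condition cannot be applied. The choice to exclude starters is sound.

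The consequence is a possible downward bias in the ICC, and an upward bias in the SEM and SDC if they use the same sample, from starters who pass the stability screen. Its size is unknown. The figures of 0.73 to 0.68 for a true ICC of 0.75, and an SEM rise of 4-13%, bound it from above within the assumed ranges. An effective screen would leave much less. The mismatch itself does not depend on those numbers.

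The conclusion assumes that the unseen questionnaire text holds no such item. The matter is confined to part of the SBQ-LC validation; the cohort and cluster analyses are untouched.

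**What to change.** Add a yes/no item on new treatment for Long COVID symptoms to the monthly schedule in Table 1.0, at least at the retest administration. Word it to cover the time since the last questionnaire, because the gap can exceed four weeks, and bring the look-back in section 10.2 into line. Use the item together with the monthly recovery item to define the stable set, and say so in section 10.2.

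If the Atom5 questionnaire already contains the item, list it in Table 1.0.

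The cost is one extra question, so slightly more questionnaire burden, and a minor amendment.
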